### Procedures for Modeling Cue-Induced Eating Behavior.

Each participant will complete two laboratory sessions, the first scheduled prior to starting medication, and the second at the end of medication treatment (week 11-14). This pre-post evaluation by medication group will provide a powerful test of medication effects. Alternatively, if the pre-treatment laboratory session cannot be schedule prior to the beginning of treatment, participants may complete the session around one month of treatment (week 4-6). If we are unable to reschedule at the HRU/CSRU, the lab session will take place at [name] in dedicated lab rooms in [name] research space. Our previous eating study (HIC# 0909005678, [name]) took place in this setting and was very successful. There will be no blood collected throughout the lab session if it occurs at [name], but baseline samples will be obtained on the 4th Floor YCCI unit. All other lab procedures will remain the same. Participants will not be excluded from the treatment study if they are not willing to do the lab sessions, or if they are not able to be scheduled for the lab sessions. Research procedures related to the treatment study (e.g., blood draws for liver function, lipids, and metabolic function) will still be drawn if lab sessions are not completed.

Laboratory sessions will be completed at the Hospital Research Unit (HRU) of the Yale Center for Clinical Investigation (YCCI) located at Yale-New Haven Hospital or the Church Street Research Unit (CSRU) at [name]. Participants will be instructed not to eat past 10:00pm the night before the laboratory session. They will arrive at the HRU/CSRU at 7:30am. At the start of the lab session, participants will have an IV cannula inserted and complete the baseline assessments listed in **Table 1**. Participants will then receive breakfast to standardize time since last food consumption. Breakfast will be a breakfast bar that is approximately 150 calories provided by the Research Team. Participants will then be food deprived for the next 3 hours. Based on our prior work, this length of food deprivation is sufficient to increase food craving. After 3 hours of food deprivation, participants are presented with preferred high-caloric snacks. Participants will be asked to take their study medication prior to the second lab session. Scheduling is limited to HRU/CSRU and participant availability.

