During a prior appointment, participants are presented with an extensive list of high-caloric salty (potato chips, peanuts) and sweet snack foods (cookies, chocolate), and are asked to select their top three salty and sweet options for a total of six options. During the lab session, participants will be presented with a standardized amount of each of their six preferred high-caloric foods. The snacks will be portioned to 750 calories of each (approximately 4-5 servings of each item). The weight of the food will be assessed at the start and end of each session, and calories consumed will be calculated from baseline evaluations of calories per gram. Each participant will receive the same presentation and amount of food across the two sessions.

Following the presentation of food, participants are then told that they can start eating at any time they wish over the next 3 hours. We model the ability to resist eating over a 3-hour period, to provide sufficient time to capture the effect of the high-caloric snack food triggering eating. Participants are informed that for each minute that they can resist eating, they will receive monetary compensation. The amount of money earned over the 3 hours starts at \$0.35 per minute, and reduces by a penny every 5 minutes. By 180 minutes, the compensation has reduced to \$0 per minute. Participants are provided this information in table format during the laboratory session. If a participant resists eating for the entire 3 hours, they will earn a total of \$31.50. Participants will be videotaped and wear a smartwatch (wearable Biosensor) synced to a research

smartphone during the eating session. The data will be coded and provide information about how fast participants eat and the order in which foods are selected.

When participants can no longer resist and decide to start eating, latency to eat will be recorded in seconds. Participants may eat as much as they wish until the end of the 3-hour ad-lib period. Measures of leptin, ghrelin, food craving, hunger, mood, and vitals will be assessed throughout the laboratory procedure (see **Table 1**). At the end of the period, participants will remain in the laboratory for an additional 1.5 hours to add a response cost if they chose not to consume any food during this period. In other words, they are not immediately able to leave the session to go eat.

**Table 1**: Procedures and assessments for laboratory sessions (also see Table 2).

PERIOD	TIMING	PROCEDURES

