### 13. **Statistical Considerations:** Describe the statistical analyses that support the study design.

Baseline demographic and clinical characteristics for the randomized groups will be compared using chi-square tests for categorical variables, and ANOVA or Kruskal-Wallis tests for continuous variables. Continuous variables will be examined for normality using normal probability plots and Kolmogorov-Smirnov test statistics. If normality is not satisfied, transformations or nonparametric alternatives will be considered. Dropouts and completers will also be compared. Primary analyses will be based on an intent-to-treat basis. Primary outcomes will be tested at the two-sided alpha 0.05 threshold. Secondary analyses will be adjusted for multiple tests using the Bonferroni correction basing the adjustment on the number of conceptually related statistical tests within each hypothesis.

Overall analysis strategy. Mixed-effects models [92] will be used to compare treatments. These models allow for different numbers of observations per subject, use all available data on each subject, and are unaffected by randomly missing data. A further advantage is the capacity to test and account for individual-difference contributions to the treatment outcomes (Cudeck, 1996; Cudeck & Klebe, 2002; Hedeker et al., 1996; Hedeker & Gibbons, 1996; Singer, 1998). They provide flexibility in modeling the correlation structure of the data. In models for each outcome in Aims 1 & 2, we will include obesity status (obese vs. non-obese) and treatment (NB vs. placebo) as between-subject effects, time (see Aim-specific study time points) as a within-subjects factor, and subject as the clustering factor. Across analysis, time-points associated with the 12-week treatment phase will be considered as primary outcomes, and all analyses will be repeated to examine change

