during the 12-month follow-up period. All possible interactions will be modeled and the following primary a priori contrast will be tested: 1) placebo NB vs. active NB. Least-square means will be plotted and compared post-hoc to interpret significant effects. Because we cannot a priori predict the shape of the response over time in each arm of the trial we will first treat time as a categorical predictor and will then test for polynomial trends over time. We will consider different error structures (e.g., AR1, CS, independence) and select the best fitting one based on Schwartz' Bayesian Criterion (BIC). We will compare dropout patterns between groups and if there are concerns of informative dropout or informative intermittent missing data, we will use pattern mixture models [93] to perform sensitivity analyses. Secondary models will include subjects with complete data. To test for assessment reactivity, we will evaluate whether biosensor assessment (yes/no; between-subject variable) moderates our primary outcomes in Aim 1 (as either a main effect, or interacting with medication). If this is found, then all subsequent analyses for Aims 1 & 2 will be limited to the sample (n=140) without the biosensor assessment.

Primary Aim 1. We will use the mixed models described above to test the effectiveness of NB medication for BED patients with and without obesity. The primary aims are to evaluate NB medication for (a) reducing binge eating frequency; and (b) in the patients with obesity, for reducing % weight loss. Significant NB main effects (regardless of obesity status) on frequency of binge eating will be considered supportive of our primary hypothesis. We also expect that NB will be associated with significantly greater reductions in % weight loss among the BED+obese group. In view of the factorial design, we will also be able to assess whether obesity status moderates reductions in binge eating frequency. These analyses will focus on 12-week outcomes. Secondary analysis will be repeated to examine change during the 12-month FU period.

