**Primary Aim 2**. To evaluate potential mechanisms underlying the effect of NB on binge eating behavior, we will first evaluate whether NB treatment changes latency to resist eating, calories consumed, leptin, ghrelin, and food craving employing the mixed models described above. If a potential mechanism demonstrates a significant time x medication effect, we will then evaluate whether improvement in the variable of interest mediates changes in frequency of binge eating over the 12-week treatment period. Following the general analytic framework outlined by Kraemer (2002), we will use the product of the coefficients method to

evaluate the relationship between the mediator, or indirect effect, and outcome. After running a regression equation to determine (1) the effect of treatment on the mediator (provides beta weight for a), we will evaluate (2) the strength of the relationship between the mediator, treatment, and outcome (provides beta b). Using MacKinnon's software PRODCLIN, we will evaluate the asymmetric confidence intervals for the product of the regression estimates (a\*b). Importantly, we note that statistical mediation is not equivalent to causation, and will be sure to appropriately limit our conclusions. Significant NB main effects in latency to resist eating, calories consumed, leptin, ghrelin, and food craving will be considered supportive of our hypothesis. Further, significant mediation of NB-related changes in lab variables on clinical outcomes (reduction in binge eating frequency) will be considered supportive of our hypothesis.

**Exploratory Aim 3**. To account for the hierarchical structure of the data, linear mixed models will be used to assess differences over time in affect and eating behaviors per day collected over a 6-week period. To evaluate potential mechanisms underlying triggers of binge eating behavior, we will first evaluate whether NB treatment changes eating behavior. We will also evaluate the time course of affect and eating behaviors to identify potential antecedents and consequences of binge eating episodes.

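### Aim 2 counts an NB main effect on the lab variables as support but opens mediation on time x medication; read literally, the main effect on latency and calories is half the end-of-treatment effect

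*Combined protocol and SAP*

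**What the plan says.** Hypothesis 2.2 (Section I, item 1) predicts that NB will help patients hold off from eating and will lower the calories they eat. Item 13, Primary Aim 2, analyses the lab variables with the mixed model set out under the overall analysis strategy. That model has treatment and obesity status between subjects and "time (see Aim-specific study time points) as a within-subjects factor", with time categorical at first. On contrasts it says: "All possible interactions will be modeled and the following primary a priori contrast will be tested: 1) placebo NB vs. active NB". No session is named.

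The Aim 2 paragraph then uses two terms for the same variables. Mediation follows "If a potential mechanism demonstrates a significant time x medication effect". Support is defined separately: "Significant NB main effects in latency to resist eating, calories consumed, leptin, ghrelin, and food craving will be considered supportive of our hypothesis". Significant mediation is listed as a further supportive result.

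The section on modeling cue-induced eating plans two lab sessions, one before medication and one at week 11-14, and adds: "This pre-post evaluation by medication group will provide a powerful test of medication effects". Each session yields one latency ("latency to eat will be recorded in seconds") and one calorie total ("The weight of the food will be assessed at the start and end of each session"). Table 1 shows leptin, ghrelin and food craving measured repeatedly within a session. If session 1 cannot be held before treatment, that section and the design overview allow it at week 4-6 on treatment. The overview considers that interval long enough for drug effects on eating to show. No analysis rule for these sessions is given.

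**The concern.** In a model with treatment, time and their interaction, the treatment main effect and the time x medication term answer different questions. When one of two time points precedes the drug, a main effect averaged over time mixes a comparison that should be null with the one of interest. The interaction isolates the change. The two can disagree for the same variable: one could be significant and the other not.

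What is at stake is which NB test answers Hypothesis 2.2. If that stays open until unblinding, the choice between two results can be made after they are seen. First sessions held on drug make it worse, because scheduling would then move both estimates.

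**Working it through.** The plan gives no effect size, SD, correlation or power for Aim 2, so there is no figure to reproduce.

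**Inputs from the plan.** Two lab sessions; one latency and one calorie value per session; 1:1 allocation; 50 per cell, so 100 per arm; two-sided 0.05.

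**Step 1: session 1 is in the model.** With one value per session, time x medication exists for latency and calories only if session 1 is a level of time.

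**Step 2: size of each term, all first sessions before drug.** The expected NB minus placebo difference is 0 at session 1 (randomisation) and d at session 2.
- Main effect, averaged equally over sessions: (0 + d)/2 = 0.5d.
- Time x medication: d - 0 = d.

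Neither result needs an SD or correlation. A simulated mixed model with the full factorial, 100 per arm, d = 0.5 SD and correlation 0.5 gave 0.250 and 0.497.

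**Step 3: on-drug first sessions.** Assume a share s of first sessions is at week 4-6 and that NB has its full effect there. The expected session-1 difference is then sd.
- Main effect: (sd + d)/2 = (0.5 + 0.5s)d.
- Time x medication: d - sd = (1 - s)d.
- At s = 0.2: 0.6d and 0.8d. At s = 1/3 both are 0.67d.
- ANCOVA with the on-drug session as baseline, slope 0.5, s = 0.2: d - 0.5 x 0.2d = 0.90d, which is biased.

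**Step 4: power, illustrative.** Assume equal SDs of 1, correlation r, large samples, and an effect for which ANCOVA at session 2 has 80% power (noncentrality 2.802). Variances per subject are (1 + r)/2 for the two-session mean, 2(1 - r) for change and 1 - r² for ANCOVA. At r = 0.5:
- scaled effect: 2.802 x sqrt(0.75) = 2.427;
- main effect: 0.5 x 2.427/sqrt(0.75) = 1.401, power about 29%;
- time x medication: 2.427/1 = 2.427, power about 68%.

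With no on-drug first sessions:

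| Correlation | Main effect | Time x medication |
|---|---|---|
| 0 | 51% | 51% |
| 0.3 | 38% | 62% |
| 0.5 | 29% | 68% |
| 0.7 | 19% | 73% |

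Letting the session-2 to session-1 SD ratio run from 0.7 to 1.3, with correlation 0.3 to 0.7, gives 15-46% and 44-80%.

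On-drug first sessions change the ranking. At r = 0.5 and s = 0.3 the main effect has 0.65 x 2.427/0.866 = 1.82, about 44%. Time x medication has 0.7 x 2.427 = 1.70, about 40%.

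**Step 5: how often the tests disagree.** At r = 0.5, equal SDs and s = 0 the two statistics are uncorrelated, so disagreement is 0.29 x 0.32 + 0.71 x 0.68, about 58%. This depends on the 80% anchor: at noncentrality 4.5 and r = 0.3 it is about 27%.

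**The case against.** The best defence is that the authors mean something else by a main effect. The overall strategy treats time points in the 12-week treatment phase as primary, and a pre-medication session lies outside that phase. A model can hold session 1 as a level of time and still test NB against placebo at session 2. The Primary Aim 1 paragraph uses a main effect to mean pooled across obesity groups, which parallels the split between Hypotheses 2.2 and 2.3. The lab section speaks of a pre-post evaluation. On that reading nothing is diluted. Nor does the plan specify an equal-weight average over time; under reference coding the treatment coefficient would be the difference at one session.

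This has force, and the intended test may well be sound. But no passage carries that definition into Aim 2, where the paragraph uses time x medication as a separate term shortly before the support rule. The post hoc comparison of least-square means interprets significant effects; it does not set the criterion.

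It is also fair that a mediation gate and a support rule may differ, because they serve different hypotheses. Naming time x medication for both would end the ambiguity. It would still leave the estimate exposed to on-drug first sessions.

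**Conclusion.** The point holds as an undefined criterion with a quantifiable consequence. The Aim 2 paragraph uses two tests for the same variables. Read literally, the one that counts as support estimates 0.5d for latency and calories when every first session is before drug. That figure rests on an equal-weight average over the two sessions. The week 4-6 option moves both terms, and its frequency is not given.

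A reader might infer more than the documents support:
- *That all five lab variables are halved.* Leptin, ghrelin and craving have several values per session, so session 1 is not forced into their models. The dilution applies to them only if both sessions enter.
- *That the main effect is always the weaker test.* Powers are equal at correlation 0, and the ranking reverses by about s = 0.3 at correlation 0.5. The 29% against 68% comparison is one assumed case.
- *That a null main effect would refute the hypothesis.* The plan does not say this and names mediation as a second supportive route.
- *That Aim 1 has the same fault.* The argument rests on the lab schedule and the two Aim 2 criteria, and the Aim 1 paragraph directs its analyses to 12-week outcomes.

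The primary clinical outcome, binge-eating frequency, is not affected.

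**What to change.** In the Primary Aim 2 paragraph, replace the main-effect criterion with one contrast: the NB minus placebo difference at lab session 2, pooled over obesity status and adjusted for a pre-treatment session 1. Use ANCOVA, or a longitudinal model with baseline means constrained equal. Let the same contrast open the mediation step. For leptin, ghrelin and craving, name the within-session value or summary to which it applies.

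Treat a week 4-6 on-drug first session as a missing baseline, never as the baseline. The constrained model handles this directly; ANCOVA would need a stated rule for missing baselines.

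The cost is SAP wording and a little analysis work, with no new visit or measurement. The loss of information is small. With an assumed 20% of such sessions and correlation 0.5, the share retained is (0.8/0.75 + 0.2)/(1/0.75) = 0.95. The noncentrality falls to 2.802 x sqrt(0.95) = 2.731, so power is about 78% instead of 80%. The change should be made before unblinding.

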4. **Research Plan:** Summarize the study design and research procedures using non-technical language that can be readily understood by someone outside the discipline. **Be sure to distinguish between standard of care vs.** research procedures when applicable, and include any flowcharts of visits specifying their individual times and lengths. Describe the setting in which the research will take place.

Overview of Study Design

This single-site, proof-of-concept, clinical trial is a double-blind, placebo-controlled, parallel group study to test the effectiveness of naltrexone + bupropion (NB) pharmacotherapy in BED patients with and without obesity. BED patients with (BMI > 30 and <50) and without obesity (BMI >21.5 and <29.9), will be randomized to NB (32 mg/day naltrexone combined with 360 mg/day bupropion) or placebo (n=50 per cell, n=200 total).

Following eligibility screening and randomization, participants will start a 12-week medication treatment period, a treatment period consistent with other BED medication trials (McElroy et al., 2016). Participants will have four weeks of up-titration: one tablet daily (Naltrexone 8mg/ Bupropion 90mg; 1 week), then two tablets daily (Naltrexone 16mg/ Bupropion 180mg; 1 week), then three tablets daily (Naltrexone 24mg/ Bupropion 270mg; 1 week), to reach the full dose of four tablets daily (Naltrexone 32mg/ Bupropion 360mg). The dosage will continue for the remainder of the 3 months. Medication will be discontinued at the end of 3 months, and patients will then be followed 12-months post-treatment to assess the durability of medication effects. The primary outcome measure is reduction in binge-eating frequency.

To evaluate correlates and mechanisms of NB on eating behavior, assessments will occur in the laboratory and in the field to optimize internal and external validity. Participants will complete human laboratory sessions ("lab sessions") before the start of medication and then during the final week of the 12-week medication period to evaluate the ability to resist eating preferred high-caloric food and subsequent overeating. During the laboratory sessions, we will evaluate potential mechanisms including eating peptides

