Baseline	7:30am	Urine pregnancy screen, breath alcohol level, CO level, height, weight, vitals,
		mood, food craving, hunger. IV inserted: Estradiol/progesterone (females only),
		liver function, lipids, glucose, insulin, and HbA1c, and overnight fasting levels of
		leptin, ghrelin. Lab 2 Only: Med level, liver function, Lipids, glucose, insulin, and
		HbA1c levels.
	8:00am	Standardized breakfast (no access to food until 11:00am = 3hours of food
		deprivation)
Deprivation	9:00am	Mood, food craving, hunger, vitals
	10:00am	Mood, food craving, hunger, vitals
Food	10:30am	Baseline 1: leptin, ghrelin
Presentation	10:45am	Baseline 2: leptin, ghrelin
	11:00am	Participant presented preferred high-caloric foods. Participant may initiate ad-lib
		eating session or earn money based on de-escalating schedule of reinforcement
		over next 180 minutes
	11:05am	Leptin, ghrelin, mood, food craving, hunger, vitals
	11:15am	Leptin, ghrelin, mood, food craving, hunger, vitals
Ad-lib	11:30am	Leptin, ghrelin, mood, food craving, hunger, vitals will be repeated every 30
Period	12:00pm	minutes during the ad-lib period
	12:30pm	
	1:00pm	**from 11:05am to 2:00pm, whenever the participant decides to 'give in' and
	1:30pm	start eating, we will collect leptin, ghrelin, mood, food craving, hunger, vitals to
	2:00pm	capture the decision point to eat (before eating starts)
Wait Period	2:45pm	Mood, food craving, hunger, vitals
& Discharge	3:20pm	Mood, food craving, hunger, vitals
	3:30pm	Discharge

Procedures for Evaluating Naturalistic Eating Behavior and Stress with Wearable Biosensors.

**Garmin Activity Tracker (Biosensor):** We are collaborating with [name] (UMass) to evaluate ambulatory stress and eating behavior during the first 6-weeks of the treatment phase. We are currently using the same system to monitor stress and alcohol consumption (HIC#2000023970; PI, [name]) and it has been adapted to monitor stress and eating behavior. During the first 6-weeks of the treatment phase, we will assess ambulatory dynamic changes in stress with a wearable biosensor and collect daily information

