### Measures:

### **Screening Measures**

- MINI International Neuropsychiatric Interview-Version 7.0 (MINI) [57] is a brief structured interview for Axis I psychiatric disorders. Validation and reliability studies have supported the MINI, including good convergence with SCID [57]. The MINI requires much less time than the SCID and reduces participant burden while providing adequate psychiatric data to characterize patients and determine exclusion criteria.
- Eating Disorder Examination Interview—16th Edition (EDE) [58] is an investigator-based interview assesses the features of eating disorders and generates eating disorder diagnoses. The EDE will be our primary method for assessing binge eating and eating disorder psychopathology. The EDE focuses on the previous 28 days, except for diagnostic items, which are rated for additional duration stipulations to address *DSM*-5 criteria for BED. The EDE assesses the frequency of different forms of overeating, including objective binge-eating episodes (OBE; i.e., unusually large amounts of food with loss of control). The EDE also comprises four scales (dietary restraint, eating concerns, weight concern, and shape concern) and a global severity score. The EDE has good psychometric properties [59], is the major outcome measure for BED RCTs [44, 60], and has good test-retest reliability.
- Body Mass Index (BMI) will be calculated using measured Height (measured once at baseline) and Weight (obtained regularly at assessment meetings).
- Lipid profiles (**Lipids**): total cholesterol, HDL-, LDL-cholesterol, triglycerides will be obtained fasting per established protocols (Anderson et al., 1995).
- Glycemic Control: HbA1c, Glucose and Mean Plasma Glucose, routine measures of average glucose control for a previous (3-month) period.
- Hepatic function panel (**Liver Function**) will be assessed for safety at the first monthly treatment visit and at the end of treatment.
- Thyroid-stimulating hormone (TSH) will be assessed if patients report any history of thyroid disease or are taking thyroid medications.
- Urine drug testing for opiates will be completed for all participants.
- Urine pregnancy testing will be assessed for female patients of child-bearing potential.
- Menstrual Cycle Data: Menstrual cycle calendar (updated regularly), hormone use, reproductive and gynecological status

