### Safety and Compliance

- Blood Pressure (**BP**) and Heart Rate (**HR**). BP readings (both systolic and diastolic) and HR will be obtained regularly at assessment meetings.
- Systematic Assessment for Treatment Emergent Effects (**SAFTEE**) [90] Adverse events will be assessed in person during study related appointments.
- Columbia Suicide Severity Rating Scale (**C-SSRS**) [91] is a semi-structured assessment intended for administration by clinicians or study staff during scheduled study visits. It explores suicidal ideation and intensity, as well as behaviors and lethality.
- Pill Counts. Participants will be asked to bring their medication to their last appointment and clinicians will count and record the number of pills remaining.
- Naltrexone and Bupropion levels plasma will be collected at weeks 4 and 12 to evaluate plasma trough levels of bupropion, naltrexone, 6-beta-naltrexol levels.

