Supplementary analysis: Retention, compliance, and sex. These analyses will provide insight into outcomes which will help us to consider directions for future research. We plan to explore whether medication compliance [plasma bupropion, naltrexone, 6-beta-naltrexol levels, pill counts], and length of time in treatment influenced our primary outcomes. Analyses described earlier will be repeated separately with a) counts of pills taken as a covariate, and b) length of time in treatment as a covariate. In participants taking active medication we will conduct a logistic regression examining area under the curve for the three plasma medication levels as a predictor of our primary outcome (frequency of binge eating) and as predictor of treatment-related change in potential mechanisms. Associations between plamsa medication levels and changes in mechanisms will provide an indication that medication is driving the change in the predictor variable. We also plan to evaluate whether sex moderates medication effects on all study outcomes. Analyses described in D.7.3. will be repeated with sex as between subject variable. We will also explore effects related to laboratory outcomes assessing estrogen and progesterone levels as covariates.

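### The plasma-level analysis names logistic regression for outcomes that are not binary, and its area under the curve is in effect the mean of two spot levels

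*Combined protocol and SAP*

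**What the plan says.** The Supplementary analysis paragraph of Section I, item 13 describes, in the active arm only, a "logistic regression examining area under the curve for the three plasma medication levels as a predictor of our primary outcome (frequency of binge eating". It then uses the same predictor "as predictor of treatment-related change in potential mechanisms", and says that associations between drug levels and mechanism changes will be taken as a sign that the drug produced those changes.

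The outcomes are defined elsewhere:

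- **Binge eating.** Overview of Study Design: "The primary outcome measure is reduction in binge-eating frequency". Under Screening Measures: "The EDE assesses the frequency of different forms of overeating, including objective binge-eating episodes", with a 28-day window.
- **Mechanisms.** Primary Aim 2 in item 13 lists "latency to resist eating, calories consumed, leptin, ghrelin, and food craving employing the mixed models described above".

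Drug levels are described in three places:

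- **Safety and Compliance measures:** "plasma will be collected at weeks 4 and 12 to evaluate plasma trough levels of bupropion, naltrexone, 6-beta-naltrexol levels". The paragraph on monitoring medication compliance gives the same two weeks.
- **Figure 2:** the drug-level row is marked at Month 1 and Month 3 and is blank at Lab #2.
- **Table 1:** at the laboratory baseline, "Lab 2 Only: Med level, liver function". The accompanying procedures state: "Participants will be asked to take their study medication prior to the second lab session".

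**The concern.** An episode count and changes in latency, calories, hormones and craving are not binary, and the paragraph does not say how any of them would become so. It cannot simply be read as shorthand for remission. Remission and relapse already have their own logistic analysis under Secondary Aims, to which this paragraph does not refer, and leptin or calories consumed have no remission version.

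The analyst would therefore choose a cut-point, a grouping or another model after the data are in. Categorising costs power in an active-arm sample that is already modest, and a cut-point chosen late is hard to defend.

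The predictor is also loosely specified. The three levels are three analytes (bupropion, naltrexone, 6-beta-naltrexol), not three sampling times. No time window, starting value or rule for a missing draw is given. A reader of the results could take an area under the curve to mean exposure over a dosing interval, which these samples do not measure.

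**Working it through.** The plan states no power, sample size or effect size for this analysis, so there is no figure to reproduce.

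**Inputs from the documents.** Active arm: 2 cells × 50 = 100. Attrition of 20% to 38% is the range quoted from earlier BED drug studies in the section on treatment completion rates. That leaves 100 × 0.80 = 80 down to 100 × 0.62 = 62. Two-sided alpha of 0.05 is stated for primary outcomes and is assumed here.

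**1. Area under the curve.** By the trapezoid rule over weeks 4 to 12, AUC = 8 × (C4 + C12)/2 = 8 × the mean of the two levels. Its correlation with the mean is exactly 1. If a zero were added at week 0 (my assumption), AUC = 4 × C4/2 + 8 × (C4 + C12)/2 = 6·C4 + 4·C12, a weighted mean of the same two levels. Either form is undefined if a draw is missing.

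**2. Information kept after a split.** For a normal outcome cut at proportion p, the relative efficiency is φ(z_p)² / {p(1 − p)}.

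| Split | Information kept |
|---|---|
| 50/50 | 0.159/0.25 = 2/π = 0.64 |
| 36/64 | 0.61 |
| 20/80 | 0.49 |
| 13/87 | 0.40 |

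The plan's Background quotes 36% and 13% as abstinence rates on another BED drug and on placebo, so those splits are not far-fetched.

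**3. Effective numbers after a median split.** 80 × 0.637 = 50.9 and 62 × 0.637 = 39.5, so about 51 down to 39.

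**4. Smallest correlation detectable with 80% power.** r = tanh{(1.96 + 0.84)/√(n − 3)}.

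| Evaluable n | Outcome kept whole | Median split |
|---|---|---|
| 80 | 0.31 | 0.38 |
| 62 | 0.35 | 0.43 |

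At n = 80 and an assumed r of 0.30, power is 78% with the outcome kept whole and 57% after a median split.

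**5. Counts rather than normal data.** Overdispersed counts were simulated 1,500 times per setting with n = 80, a rate ratio of 0.67 per SD of exposure, mean counts of 4 to 8 and gamma shape of 0.7 to 1.0. All of these are assumptions, not plan figures.

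| Model | Power |
|---|---|
| Quasi-Poisson count model | 75–88% |
| Logistic, median split | 42–61% |
| Logistic, abstinence | 17–23% |

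**The case against.** Four stronger readings are tempting, and the documents do not support them.

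**That the analysis cannot be run, or that no area under the curve exists.** A two-point area is computable. It adds nothing to the mean and carries a misleading label. That is a matter of definition, not an impossibility.

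**That following the text forces a two-way split with a 36% loss.** Ordinal logistic regression accepts grouped counts or change scores, and in simulation at n = 80 a five-level version had power between the count model and the median split. The plan does not say ordinal, but neither does it mention a median split. The 64% figure assumes a normal outcome, whereas binge frequency is a count. The range of 62 to 80 comes from earlier studies and is not the number who will have both draws. Laboratory sessions are optional, so numbers for the mechanism outcomes may be lower.

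**That the end-of-treatment level is not a trough.** This depends on which draw is meant. Figure 2 places the level at Month 3 and not at Lab #2, although it marks liver function at Lab #2. Table 1 places a level at Lab 2. If these are one draw, the request to take medication before the session raises the question. If they are separate draws, it does not apply to the Month 3 level. No dose time is given either way.

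**That the Aim 2 conclusions depend on this analysis.** The criteria for support under Primary Aim 2 are drug effects on the laboratory measures and mediation, without plasma levels. The plan also promises restraint about causation there, and presents the supplementary work as exploratory.

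What remains is that the model named does not fit the outcomes named, and no reading in the text repairs it.

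**Conclusion.** Wrong as written, with low to moderate severity. The mismatch between model and outcome is plain from the text and rests on no assumption. The exposure summary is mislabelled and incompletely defined rather than invalid.

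The size of the loss is illustrative only. With a median split of a normal outcome, 62 to 80 evaluable patients would act like about 39 to 51. More uneven splits lose more, and an ordinal grouping would lose less than a median split.

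The primary treatment comparison is unaffected. The point still matters because the plan would read an association between drug levels and mechanism change as evidence that the drug is responsible. A null from a needlessly weak model, or a positive result at a cut-point chosen late, would inform that reading badly.

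**What to change.** **Models.** Specify a negative binomial model for the month-3 EDE binge-episode count, with quasi-Poisson only as a pre-stated fallback if it does not converge. Specify a linear model for each mechanism change. Adjust each for the baseline value of its outcome and for obesity stratum. Keep logistic regression for the remission endpoint already listed under Secondary Aims.

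**Exposure.** Define it per analyte as the mean of the week-4 and week-12 levels, and drop the term area under the curve. State how undetectable values are handled; they are plausible in the non-adherent patients whom a compliance analysis concerns, and a log transform alone would fail on zeros. State what happens when one draw is missing, for example using the available level and repeating the analysis in those with both.

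**Sampling.** Reconcile the Safety and Compliance measures, Figure 2, Table 1 and the laboratory procedures on whether the Lab 2 level is the week-12 level and whether it is a trough. Use time since last dose as a covariate where it was recorded. The project dates run from September 2017 to September 2024, so it may not be recoverable for draws already taken, and the analysis should not depend on it.

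**Cost.** SAP wording only, plus a recorded dose time for any draws still to come.
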